6.1.3. Follow Up Period

The follow-up period is defined from Day 29 to Month 6. Subjects will be followed at 3 months, and 6 months, or until loss to follow-up, death, or withdrawal from study, whichever occurs first.

The study will be conducted in compliance with ICH Good Clinical Practices (GCPs) and in concordance with local Health Authority regulations.

The End of Trial is defined as either the date of the last visit of the last subject to complete the post treatment follow-up, or the date of receipt of the last data point from the last subject that is required for primary, secondary and/or exploratory analysis, as specified in the protocol, whichever is the later date.

6.1.4. Hospital Discharge

Hospital discharge is defined as the day a hospitalized subject is discharged. Hospital Discharge visit should be performed if a hospitalized subject is discharged on any day other than a scheduled study visit day.

Subjects who were treated in the Phase 1 portion of the study may be discharged on the day following the final planned CYNK-001 infusion (i.e., discharged on Study Day 8, where infusions occur on Days 1, 4, and 7 or discharged on Study Day 5 if only two doses were received on Days 1 and 4.)

As part of discharge criteria, the study team should assess for further monitoring of subjects who may be experiencing toxicity of Grade 3 and above (either related or unrelated to CYNK-001) at the time of discharge and consult with the treating physician and clinical site study team. The decision to discharge a subject should be in consultation with the treating physician. Physicians should follow best clinical practice to determine appropriate timing of hospital discharge.

Upon discharge, plans should be made for appropriately delegated staff to have telephone contact with subjects every day between hospital discharge through at least Day 15 visit for safety/AE monitoring. The discharge plan should include follow-up visit schedule as well as planned telehealth visit schedule.

Upon discharge, subjects will be provided with a thermometer, pulse oximeter, and blood pressure monitor for at home collection of temperature, oxygen saturation, and blood pressure with written instructions on their use as well as expectations for self-monitoring. These daily measurements will be reported via telephone to the clinical staff during each daily telehealth visit. During these daily telehealth visits, subjects are to report any new symptoms or worsening of symptoms associated with previously identified adverse events and will also provide the study team with daily vital sign measurements. Any vital signs outside of normal range will be escalated to the clinical site study team and evaluated for appropriate management.

The subject will be asked during each call to report any new or worsening symptoms that could be consistent with adverse events since the previous visit or telephone call. The investigator (or appropriately delegated study staff) will determine if medical attention or an unscheduled clinic visit is required. Each telephone call should be carefully documented with date and time of the call in the source documents and reported as appropriate.

Alternative person to contact in case of possible emergency or for planned daily calls from clinical site staff should also be collected prior to hospital discharge.

Consultation between the Medical Monitor and appropriately delegated site staff should occur every other day after hospital discharge up to Day 15 visit for ongoing review of the subject's clinical status. This communication may occur via telephone contact or written message (i.e., email) and should be documented accordingly.

6.1.5. Early Termination

Early Termination is defined as a subject who does not complete the 6-month Follow up visit. Early termination may be due to medical discharge without follow-up, loss to follow-up, withdrawal by a subject, or death.

6.2. Number of Subjects

This study will enroll up to 86 subjects, with 14 subjects in the Phase I portion and up to 72 subjects in the Phase II portion with 36 subjects given CYNK-001 and other 36 subjects who will be treated with the best supportive care only.

6.3. Dose Limiting Toxicity (DLT) Definition

Known pathologies associated with COVID-19 will be carefully considered and differentiated from potential CYNK-001-related effects in order to identify CYNK-001 related toxicities. Adverse events occurring up to Day 28 from the first dose of the CYNK-001 infusion will be included in the dose-limiting toxicity (DLT) determination.

A DLT is defined as the development of any new (not pre-existing) events:

- Grade 4 or 5 event in any organ system
- Grade 4 > 24 hour (Due to known organ damage associated with the COVID-19) in the following organ systems:
 - Cardiac
 - Pulmonary
 - Hepatic
 - Renal
 - Central Nervous System (CNS)
- Grade 3 or above allergic reaction that is suspected to be related to CYNK-001.
- Grade 3 or above GvHD event occurring within the first 28 days following CYNK-001 infusion (to Study Day 28).
- Grade 3 or above CRS event occurring within the first 28 days following the first CYNK-001 infusion (to Study Day 28).

All above events to be identified in discussion with the clinical study Medical Monitor and reportable to Drug Safety.

The events will be assessed for the first 3 subjects in Phase I and per the study stopping rules for the remaining subjects. Any such findings will be forwarded to the DMC for recommendation, review and confirmation as to whether or not the maximal tolerated dose (MTD) has been exceeded. If the MTD is confirmed by the DMC, no further CYNK-001 administration will occur within that dose level or at any higher dose level. For the remaining 11 subjects, DMC will be convened if the safety stopping rule is met. Overall, in case of 2 out of the 6 subjects had

experienced DLTs in the Phase I portion of this study, the DMC will be convened for safety evaluation.

During Phase II portion of the study, DMC will be convened at midpoint (after 18 subjects have received treatment) to evaluate safety for adverse event of interest such as shock, ARDS, and death in the treatment group versus the control group.

MTD is defined as the highest CYNK-001 dose level wherein it was deemed safe per the defined stopping rules or if the DMC recommends stopping the study due to DLTs suspected to be related to CYNK-001.

6.4. Treatment Assignment

Phase I:

Upon confirmation of eligibility during the Screening Period, eligible subjects will be sequentially assigned to the CYNK-001 group at the time of eligibility based on treatment slot availability.

Dose Level cohorts:

- Dose Level 1: CYNK-001 with an initial IV dose of 150×10^6 cells on Day 1 followed by 600×10^6 cells CYNK-001 IV on Days 4 and 7. After the first dose, subsequent infusions on Days 4 and 7 will be provided only if no toxicity of \geq Grade 3 (either related or unrelated to CYNK-001) is observed for each subject. If any such \geq Grade 3 toxicity is observed, the second and third doses will be delayed up to 48 hours until the noted event is resolved or reduced to Grade 1 toxicity level.
- Dose de-escalation Level -1: CYNK-001 with an initial IV dose of 150×10^6 cells on Day 1 followed by 600×10^6 cells CYNK-001 IV on Day 7 will be implemented due to potential safety concerns per the DMC recommendation.

A total of 14 subjects will be treated in the Phase I portion of the study.

Phase II:

For the Phase II portion of the study, up to 72 subjects will be randomized into the study with 1:1 ratio to either CYNK-001 or the control arm (best supportive care). The Phase II portion of the study is a randomized, open-label, multi-site study. Subjects will be randomized into either CYNK-001 group or Control group with 1:1 ratio stratified by age (< 45 vs. ≥ 45 years old).

6.5. Dose Adjustment Criteria

Dose adjustments may occur if clinically indicated by the treating physician. In general, the following should be followed:

- Dose reductions are not permitted in this study. If any DLTs were observed, the dose de-escalation treatment with reducing frequency of doses will be implemented per the DMC recommendation.
- Should dose delays for CYNK-001 be required:

- Day 1 will be the date of initial dose
- Day 4 dose may be delayed up to 48 hours
 - For non-safety reasons: If delayed longer than 48 hours, Day 4 dose will be skipped., and the subject will receive the Day 7 dose. If the Day 4 dose is given within 48 hours, the Day 7 dose will be delayed for three days from the actual day of when Day 4 dose was given (Ex: if Day 4 dose is given on Day 5, then Day 7 dose will be given on Day 8)
 - For safety reasons: Day 4 dose could be delayed if \geq Grade 3 toxicity is observed after the first dose. In such cases, Day 4 dose is provided only if the event is resolved or reduced to Grade 1 toxicity level. If the toxicity did not resolve within 48 hours, the Day 4 dose will be skipped. If the Day 4 dose is given within 48 hours, the Day 7 dose will be delayed for three days from the actual day of when Day 4 dose given.
 - If the subject has worsening of illness, study medication will be stopped.
- Day 7 dose may be delayed up to 48 hours:
 - For non-safety reasons: If delayed longer than 48 hours, the subject will not receive additional therapy.
 - For safety reasons: If Day 4 dose was delayed but given within 48 hours of planned Day 4, then the Day 7 dose will be delayed for three days from the actual day of when Day 4 dose was given.

If Day 4 dose was given as planned, Day 7 dose could be delayed if \geq Grade 3 toxicity is observed after the second dose. If Day 4 dose was skipped, Day 7 dose could be delayed if \geq Grade 3 toxicity is still observed after the first dose. In such cases, Day 7 dose is provided only if the event is resolved or reduced to Grade 1 toxicity level. If the toxicity did not resolve within 48 hours of the scheduled day, the Day 7 dose will not be administered.
 - If the subject has worsening of illness, study medication will be stopped.
- All subjects who receive any amount of CYNK-001 will be followed to 6 months or until loss to follow-up, death, or withdrawal from study, whichever occurs first.
- If subject has been found to be SARS-CoV-2 negative by rRT-PCR or the third dose is skipped per protocol allowances, and has received two doses of CYNK-001, the third dose is not mandatory. The subject may be discharged one day following the final planned dose of CYNK-001.

Consultation with the Medical Monitor is required prior to each CYNK-001 infusion if there is:

- An increase in supplemental oxygen of greater than or equal to 50% from baseline (for first CYNK-001 infusion) or from level at prior CYNK-001 infusion (for second and third CYNK-001 infusion) resulting in oxygen use of greater than 8L.

-or-

- A change in the mode of supplemental oxygen delivery with the intention to deliver oxygen more efficiently.

The Medical Monitor will escalate to the Sponsor clinical and safety teams as appropriate per GCP guidelines to advise if a subject who is experiencing rapid worsening of disease should proceed to first or subsequent CYNK-001 infusion.

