6.6. Duration of Study Participation

6.6.1. Treatment Discontinuation

Discontinuation from study medication does not mean discontinuation from the study, and remaining study procedures should be completed as indicated by the study protocol. If a clinically significant finding is identified (including but not limited to changes from baseline) after enrollment, the investigator or qualified designee will determine if any change in participant management is needed. Any new clinically relevant finding will be reported as an AE. The following events are considered sufficient reasons for discontinuing a subject from study medication:

- If any clinical AE, laboratory abnormality, or other medical condition or situation occurs such that continued treatment with study medication would not be in the best interest of the participant.
- If the participant meets an exclusion criterion (either newly developed or not previously recognized) that precludes further study participation. Discussion with the Medical Monitor is recommended.
- Worsening of illness which requires discontinuation of study medication at the discretion of the treating physician.
- Subject withdrawal from treatment (subject no longer wants to receive study medication but is willing to have additional data collected), which must be documented in subject's medical record. It must be confirmed in documented communications whether or not AEs are leading the subject's choice to withdraw from the study medication.
- Death
- Protocol violation; discussion with the Medical Monitor is recommended.
- Pregnancy
- Loss to follow-up
- Completion of study treatment according to the study protocol.

Reason for study treatment discontinuation must be recorded in the electronic case report form (eCRF) and source documents.

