14.11.2. Data Monitoring Committee (DMC)

A DMC will monitor the safety and efficacy information to ensure subject safety in accordance with a separate charter. The DMC may be comprised of external members who may not be involved in the day-to-day activities of the CYNK-001 study team but will be physicians and/or Clinical Research Experts with experience treating coronavirus infections and/or clinical trial involvement with this specific subject population. The DMC will recommend whether dose de-escalation is required, whether modifications to the protocol design are necessary or whether to end dosing and/or further enrollment to the study is required. The DMC will make their determinations based on available clinical data. The decisions of the DMC will be documented in meeting minutes.

An initial DMC meeting to introduce the DMC members to the Celularity study team, relevant other parties and provide an overview of the overall study plan with applicable documentation will be conducted. The DMC will be convened for subsequent meetings:

- Upon completion of 24 hours after the final dose was provided to the 3rd subject in the Phase I portion of the study to evaluate the safety data.
- Upon an event that met the safety study stopping rules in both Phase I and Phase II of the study ([Section 14.10](#)).
- After Day 15 of the final subject treated in the Phase I portion of the study is complete, DMC will meet for review of safety and efficacy data and to recommend moving forward with the Phase II portion of the study.
- Upon completion of the study.
- In the event that during the course of the Phase I or Phase II portions of the study, even if a single subject experiences an event listed below, the DMC Chair will be notified within 24 hours of the sponsor being informed. The DMC chair may review the case and if deemed necessary request that a meeting be convened to evaluate the event. If specified, the site may be placed on investigational medicinal product (IMP) treatment hold until the event is investigated.
 - A DLT event during 28 days from first dose of CYNK-001 infusion (to Study Day 28).
- When the DMC chair requests an ad hoc meeting (e.g., when an Urgent Safety Measure requires).
- Closed session may be held during the DMC meeting per request from the DMC Chair.

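### Protocol Sections 6.5, 6.6.1, 12.1.7 and 14.10 conflict on the next infusion when a subject's illness worsens, and 6.5 does not say which of two rules governs Day 4 after a DLT

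*Protocol*

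**What the plan says.** On worsening of illness the protocol speaks in three ways.

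- Section 6.5, under the Day 4 dose and again under the Day 7 dose (repeated in the Synopsis, Dose Modifications): "If the subject has worsening of illness, study medication will be stopped".
- Section 6.5, closing paragraphs (repeated in substance in 12.1.7 and 14.10): "Consultation with the Medical Monitor is required prior to each CYNK-001 infusion if there is" one of two listed changes in oxygen support. The Medical Monitor then escalates to the sponsor "to advise if a subject who is experiencing rapid worsening of disease should proceed to first or subsequent CYNK-001 infusion".
- Section 6.6.1, among the reasons sufficient for discontinuing study medication: "Worsening of illness which requires discontinuation of study medication at the discretion of the treating physician".

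On toxicity, Section 6.5 has two further rules. The first bullet covers DLTs: "If any DLTs were observed, the dose de-escalation treatment with reducing frequency of doses will be implemented per the DMC recommendation". The Day 4 bullet covers any toxicity of Grade 3 or higher after the first dose, with a delay of up to 48 hours: "In such cases, Day 4 dose is provided only if the event is resolved or reduced to Grade 1 toxicity level". If the event does not settle in that time, the Day 4 dose is skipped. Section 6.3 counts Grade 3 or higher CRS, and a Grade 3 or higher allergic reaction suspected to be related to CYNK-001, as DLTs.

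**The concern.** A stopping rule and a rule for considering whether to proceed cannot both govern the same subject unless one is stated to be the exception. Here they stand in the same section, and a third provision gives the decision to someone else. The investigator who must decide on the next infusion of 600 million cells has no way to tell from the text which applies. This is first a matter of patient safety, in what Section 4.4 describes as the first study of the product in this disease.

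It also bears on the Phase I data. The number of doses a worsening subject receives depends on which sentence is followed. The Synopsis requires at least two doses for efficacy assessment, whereas SAP 13.1.1 bases Phase I efficacy on the safety population. If the Synopsis condition is applied, the choice of rule after Day 1 also decides whether that subject can be assessed for efficacy, and Section 14.9 allows no replacement.

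The DLT overlap is a smaller problem of the same kind: two rules can be met by one event, and nothing says which comes first while DMC advice is awaited.

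**Working it through.** No sample-size or power figure is involved. The check sets the provisions side by side and adds up cells under each route.

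**Step 1. Worsening: who decides, and what follows.**

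| Provision | Infusions covered | Outcome | Decision-maker |
|---|---|---|---|
| 6.5 dose-delay bullets; Synopsis | Day 4 and Day 7 | stop | none: automatic |
| 6.5 closing text; 12.1.7; 14.10 | first or any later one | may proceed | Medical Monitor, with sponsor advice |
| 6.6.1 | any | may stop | treating physician |

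The first infusion is outside the mandatory stop, which appears only under Days 4 and 7. The second row covers later infusions too, so the conflict is confined to the second and third.

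**Step 2. Can one subject meet more than one row?** Rapid worsening is, on an ordinary reading, a form of worsening. Appendix D gives an example. A move from nasal prongs (score 4) to high-flow oxygen (score 5) crosses from mild to severe hospitalized disease. It is also a change in mode of delivery, which, if made to deliver oxygen more efficiently, is one of the two consultation triggers. If it counts as worsening, 6.5 stops treatment; as a trigger, 6.5 opens a discussion of whether to proceed; under 6.6.1 the treating physician chooses. The protocol does not define worsening of illness or rank the provisions.

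**Step 3. Size for worsening.** Inputs (Section 6.4): 150 million cells on Day 1, 600 million on each of Days 4 and 7.

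- Full schedule: 150 + 600 + 600 = 1,350 million.
- Worsening between Days 1 and 4: stopped at 150 million, or up to 1,350 million if allowed to proceed to both later doses.
- Worsening between Days 4 and 7: stopped at 150 + 600 = 750 million, or 1,350 million.
- Ratio of the next dose to the last: 600/150 = 4 after Day 1; 600/600 = 1 after a Day 4 dose has been given.

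**Step 4. DLT overlap.** Take Grade 3 CRS after Day 1. It is a DLT (6.3) and a Grade 3 toxicity (6.5).

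- Hold route, event down to Grade 1 within 48 hours: Day 4 dose given by Day 4 + 2 = Day 6, then the third dose; planned total 1,350 million.
- Hold route, event not settled in time: Day 4 skipped; if the Day 7 dose is given, 150 + 600 = 750 million.
- Reduced-frequency schedule (Level -1 in 6.4): Days 1 and 7 only; 150 + 600 = 750 million.

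The routes differ when the event settles in time: Day 4 is given under one and omitted under the other. Both still include a 600 million cell infusion. The second depends on a DMC recommendation, and 6.5 does not say what holds for that subject in the meantime.

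**Step 5. Day 7 after a delayed Day 4.** Among the safety-reason branches for the Day 7 dose, the on-time and skipped Day 4 branches carry a Grade 3 check. The delayed branch states only a three-day shift. Sections 6.1.2 and 6.4 condition the Day 4 and Day 7 infusions on the absence of Grade 3 or higher toxicity, so the check applies there too. This is a wording mismatch, not a missing safeguard.

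**The case against.** The best defence of the worsening text is that 6.5 opens by deferring to clinical indication and describing its bullets as general guidance, that the Medical Monitor route is advisory and central, and that 6.6.1 only lists acceptable reasons for discontinuation. That softens the conflict but does not settle it. The bullets are worded as mandatory, the later text expressly reaches infusions after the first, and no sentence makes one an exception to the other.

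On DLTs the defence is stronger. The reduced-frequency schedule appears in 6.4 as a dose level, adopted on DMC recommendation, while the 48-hour hold is applied subject by subject. They may be meant to work at different levels. The protocol also requires the DMC to be convened for any DLT in the first three subjects (14.10), and its chair to be notified of every DLT within 24 hours of the sponsor being informed, with a site hold possible (14.11.2). What remains is silence on precedence. After the first three subjects, a single DLT leads to a review that is optional: "The DMC chair may review the case and if deemed necessary request that a meeting be convened to evaluate the event".

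Several stronger readings may tempt a reader, and the documents do not support them:

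- **Stop versus a four-fold dose after a DLT.** Section 6.5 contains no stop instruction for a DLT. The four-fold step is the planned Day 1 to Day 4 increase for every subject, not a product of the ambiguity.
- **Different treatment at different sites.** This is possible under 6.6.1 but inferred; the Medical Monitor route is central.
- **A DMC that cannot act in time.** The two-week lead for data outputs concerns scheduled meetings; ad hoc meetings are provided for.
- **A third dose on Day 11, outside the visit window.** This needs an assumption about which day counts as scheduled, and the relevant footnotes to Table 3 are not in the text available.
- **An oxygen trigger that is too lax.** That questions a clinical threshold and is not a contradiction.
- **A DLT rate that cannot be interpreted.** Nothing in the documents or the arithmetic shows this.

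**Conclusion.** The worsening conflict stands. For the second and third infusions the protocol gives a mandatory stop, a sponsor-advised decision and a physician's discretion for what can be the same subject, with no definition and no precedence. At the level of one subject, the spread is 150 versus up to 1,350 million cells if worsening follows Day 1, and 750 versus 1,350 million if it follows the Day 4 dose. This assumes that rapid worsening falls within worsening of illness and that no other rule withholds a dose.

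The DLT point stands only as a secondary gap in precedence: Day 4 given or omitted, 1,350 versus 750 million planned cells, when the event settles within 48 hours and the DMC has not yet advised. The Day 7 wording needs alignment only.

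How many subjects were affected cannot be derived from the documents. SAP Section 15 records that the trial closed after seven subjects were enrolled and dosed in Phase I, so reconciliation now matters mainly for reporting those subjects and for any reuse of this protocol text. In a protocol still dosing, it should be resolved before the next infusion.

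**What to change.** The passages must be reconciled; the sponsor's clinicians decide the content.

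1. Use one rule for worsening of illness, with worsening defined and one decision-maker named, in identical terms in the Synopsis (Dose Modifications) and Sections 6.5, 6.6.1, 12.1.7 and 14.10.
2. State in 6.5 whether a subject whose event meets the 6.3 DLT definition follows the 48-hour hold or the DMC route, and what applies to that subject until the DMC has advised.
3. Align the delayed-Day-4 wording for the Day 7 dose with the general Grade 3 rule in 6.1.2.

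The cost is amendment wording, with no added visits or subjects. For the seven subjects already dosed, the brief clinical study report can state, for any infusion withheld or released after worsening or a DLT, which provision was followed. Section 6.6.1 already requires discontinuation reasons on the eCRF, so only decisions to proceed may need to be traced in source records.
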